8.3 ADVERSE EVENTS AND SERIOUS ADVERSE EVENTS

8.3.1 DEFINITION OF ADVERSE EVENTS (AE)

Adverse event means any untoward medical occurrence associated with the use of an intervention in humans, whether or not considered intervention-related (21 CFR 312.32 (a)).

An adverse event can therefore be any unfavorable and unintended sign (including an abnormal laboratory finding, for example), symptom, or disease temporally associated with the use of a medicinal product, whether or not considered related to the medicinal product. This includes any occurrence that is new in onset or aggravated in severity or frequency from the baseline condition, or abnormal results of diagnostic procedures, including laboratory test abnormalities.

8.3.2 DEFINITION OF SERIOUS ADVERSE EVENTS (SAE)

An adverse event (AE) or suspected adverse reaction is considered "serious" if, in the view of either the investigator or sponsor, it results in any of the following outcomes:

- death,
- a life-threatening adverse event,
- inpatient hospitalization or prolongation of existing hospitalization,
- a persistent or significant incapacity or substantial disruption of the ability to conduct normal life functions, or
- a congenital anomaly/birth defect.

Important medical events that may not result in death, be life-threatening, or require hospitalization may be considered serious when, based upon appropriate medical judgment, they may jeopardize the participant and may require medical or surgical intervention to prevent one of the outcomes listed in this definition. Examples of such medical events include allergic bronchospasm requiring intensive treatment in an emergency room or at home, blood dyscrasias, or convulsions that do not result in inpatient hospitalization, or the development of drug dependency or drug abuse.

8.3.3 CLASSIFICATION OF AN ADVERSE EVENT

8.3.3.1 SEVERITY OF EVENT

Event severity will be assigned according to the Investigator's assessment.

Severity Grade for Parameters Not Identified in the Grading Table:

The functional table below should be used to grade the severity of an AE that is not specifically identified in the grading table. In addition, all deaths related to an AE are to be classified as Grade 5.

PARAMETER	GRADE 1 MILD	GRADE 2 MODERATE	GRADE 3 SEVERE	GRADE 4 POTENTIALLY LIFE-THREATENING
Clinical adverse event NOT identified elsewhere in the grading table	Mild symptoms causing no or minimal interference with usual social & functional activities with intervention not indicated	Moderate symptoms causing greater than minimal interference with usual social & functional activities with intervention indicated	Severe symptoms causing inability to perform usual social & functional activities with intervention or hospitalization indicated	Potentially life-threatening symptoms causing inability to perform basic self-care functions with intervention indicated to prevent permanent impairment, persistent disability, or death

8.3.3.2 RELATIONSHIP TO STUDY INTERVENTION

Attribution/Assessment of Causality is a determination that describes the relationship or association of the study product with an adverse event.

This assessment of causality or relationship of AEs to the study drug is provided by the Investigator and is determined by 1) temporal relationship of the event to the administration of study drug; 2) whether an alternative etiology has been identified, and 3) biological plausibility. Causality must be assessed separately for each study drug.

The causality assessment categories that will be used for this study are described below.

1. Causality assessments that are considered **not related** to study drug:

a. *Not related:*

The event is related to an etiology other than the study drug (the alternative etiology must be documented in the participant's medical record).

If an SAE is considered "unrelated" to study drug, the Investigator should offer his/her clinical opinion as to what factor(s), agent(s), or process(s) were the likely causative mechanism for the event.

2. Causality assessments that are considered **related** to study drug:

a. *Possible:*

There is an association between the event and the administration of the study drug and there is a plausible mechanism for the event to be related to study drug; but there may also be alternative etiology, such as characteristics of the participant's clinical status or underlying disease.

b. *Probable:*

There is an association between the event and the administration of study drug, a plausible mechanism for the event to be related to the study drug, and the event could not be reasonably explained by known characteristics of the participant's clinical status or an alternative etiology is not apparent.

c. *Definite:*

There is an association between the event and the administration of study drug; a plausible mechanism for the event to be related to the study drug, causes other than the study drug have been ruled out, and/or the event re-appeared on re-exposure to the study drug.

8.3.3.3 EXPECTEDNESS

The study PI (or designee) will be responsible for determining whether an adverse event (AE) is expected or unexpected. An AE will be considered unexpected if the nature, severity, or frequency of the event is not consistent with the risk information previously described for the study intervention or is not listed in the most current IBs for the study intervention.

8.3.4 TIME PERIOD AND FREQUENCY FOR EVENT ASSESSMENT AND FOLLOW-UP

The occurrence of an adverse event (AE) or serious adverse event (SAE) may come to the attention of study personnel during study visits and interviews of a study participant presenting for medical care, or upon review of medical record.

The study unsolicited AE reporting period will be from enrollment (Day 0) through the end of study visit. During Step 1 (period between consent and Day 0), any AE that occurs will be collected as concurrent medical history (pre-existing condition) and not as an AE, unless it is due to a protocol-related procedure (leukapheresis).

All AEs including local and systemic reactions not meeting the criteria for SAEs will be captured in the research record on the appropriate form. Information collected includes:

- Event description,
- Time of onset,
- Study PI's (or designee's) assessment of severity, relationship to study product and expectedness,
- Time of resolution/stabilization of the event.

All AEs occurring while on study must be documented appropriately regardless of relationship. All AEs will be followed to adequate resolution.

Any medical condition that is present at the time that the participant is screened will be considered baseline and not reported as an AE. However, if the study participant's condition deteriorates at any time during the study, it will be recorded as an AE.

Changes in the severity of an AE will be documented to allow an assessment of the duration of the event at each level of severity to be performed. AEs characterized as intermittent require documentation of onset and duration of each episode.

The study research coordinator will record all reportable events with start dates occurring any time on or after the enrollment visit until 7 (for non-serious AEs) or 30 days (for SAEs) after the last day of study participation. At each study visit, the research coordinator will inquire about the occurrence of AE/SAEs since the last visit. Events will be followed for outcome information until resolution or stabilization.

Clinical Laboratory Changes:

Safety laboratory assessments will be carried out locally at UNC and evaluated by the Investigator (or designee) to ensure participant safety. The Investigator (or designee) is responsible for reviewing the results of all laboratory tests as they become available.

- Laboratory values that fall outside of a clinically accepted reference range or differ significantly from previous values must be evaluated for clinical significance by the Investigator (or designee). The Investigator (or designee) may repeat the laboratory test or request additional tests to verify the results of the original laboratory tests.
- If the Investigator (or designee) determines the laboratory value is an abnormal change from baseline and is of clinical significance for that participant, it is considered an AE.
- Generally, Grade 1 and Grade 2 laboratory findings need not be reported as AEs unless deemed clinically significant by the Investigator (or designee).
- Consistent with the DAIDS designation of Grade 3 events as severe or medically significant and Grade 4 events as life-threatening, Grade 3 and Grade 4 laboratory findings should be reported as AEs or SAEs, as appropriate.

- The test result or finding should be reported as the AE. Such laboratory values should generally be recorded as “increased” or “decreased” (e.g., change from baseline potassium of 5.0 to 3.5 mEq/L = potassium decreased).

The study PI (or designee) is responsible for appropriate reporting of adverse events to the regulatory authorities. The study PI (or designee) will also report all suspected unexpected serious adverse reactions. The study PI (or designee) must report suspected unexpected serious adverse reactions to the UNC IRB, unless otherwise required and documented by the UNC IRB.

8.3.5 ADVERSE EVENT REPORTING

Adverse events will be graded according to the DAIDS Table for Grading the Severity of Adult and Pediatric Adverse Events (DAIDS AE Grading Table), corrected Version 2.1, July 2017, on the DAIDS RSC website at <http://rsc.tech-res.com/clinical-research-sites/safety-reporting/daids-grading-tables>

Participants will be monitored for adverse events. Toxicities will be characterized in terms including duration, intensity, and time to onset. Safety endpoints will include all adverse experiences, in addition to laboratory safety assessments, and vital signs. All AEs will be recorded on the appropriate study form. All AEs will be recorded in the database if any of the following criteria have been met:

- Study-related grade ≥ 1 AEs
- Grade ≥ 3 AEs
- Autoimmune-related AEs regardless of grade
- HIV viral loads ≥ 50 copies/mL
- Infusion reactions regardless of grade
- AEs that led to a change in study intervention regardless of grade
- AEs meeting SAE definition or EAE (Expedited Adverse Event) reporting requirement

Grade 1 or 2 Toxicity

Participants who develop a Grade 1 or 2 AE or lab toxicity that occurs following a VRC07 infusion or dose of VOR dosing that is thought to be possibly, probably, or definitely related to study treatment should be discussed with the study team. Grade 1 or 2 AEs that may be related to the VRC07-523LS or VOR should be handled according to standard clinical practice and documented. Participants who experience a Grade 1 or 2 AE that is judged related to the study treatments by the study PI (or designee), may continue study treatment at the discretion of the study PI (or designee).

Participants who experience a Grade 1 or 2 AE that is judged not to be related to the study drug/product by the study PI (or designee), may continue study treatment at the discretion of the study PI (or designee).

Grade 3 Toxicity

For participants who develop a Grade 3 AE following administration of VRC07-523LS or VOR that is judged by the study PI (or designee) to be at least possibly study treatment-related, the protocol team, inclusive of the DAIDS Medical Officer, must be notified within 24 hours. Participants experiencing Grade 3 AEs should be followed closely and if the AE does not return to Grade ≤ 2 within 2 weeks, the study team should again be notified within 24 hours and the SMC will be notified. Continued receipt of study

products is at the discretion of the study PI (or designee) in consultation with the protocol team and the SMC.

For participants who experience a Grade 3 AE that is judged not related to the study treatment by the investigator, continued study participation is at the discretion of the study PI (or designee) in consultation with the protocol team and SMC.

Grade 4 Toxicity

For participants who develop a Grade 4 AE following administration of VRC06-523LS or VOR that is judged by the study PI (or designee) to be at least possibly study treatment-related, the protocol team, the DAIDS Medical Officer and SMC must be notified within 24 hours. Participants experiencing Grade 4 AEs should be followed closely with additional clinical assessments and laboratory testing as clinically indicated. If the AE does not return to Grade ≤ 2 within 2 weeks, the protocol team and SMC should again be notified within 24 hours.

All study treatments will be discontinued in the event of Grade 4 AEs possibly related to study treatment.

Local or Systemic Reactions to VRC07-523LS

Grade 1 or 2

Local reactions of mild (Grade 1) or moderate (Grade 2) severity will usually resolve spontaneously. If needed, they may be managed with local application of cold packs, oral acetaminophen, oral non-steroidal anti-inflammatory agents, or a combination of these measures as appropriate.

NOTE: Topical steroids should not be applied to the infusion site.

Grade 3 or 4

For severe (Grade 3) or potentially life-threatening (Grade 4) local reactions, the protocol team, inclusive of the DAIDS Medical Officer, must be notified within 24 hours. For Grade 4 local reactions, definitive medical and/or surgical intervention should be undertaken as appropriate. Further infusions will not be administered.

Systemic Reactions

The protocol team, inclusive of the DAIDS Medical Officer, must be contacted within 24 hours for any non-local Grade 3 or 4 systemic reactions thought definitely, possibly, or probably related to the VRC07-523LS infusion or the administration of VOR doses. Further infusions and VOR doses will not be administered.

If an adverse event of special interest (AESI) occurs (see section 8.3.8), the study coordinator, in collaboration with the study PI (or designee), will evaluate the severity and seriousness of the AE and the relationship to the study treatment, and will document the findings.

The protocol team, inclusive of the DAIDS Medical Officer, should be contacted within 24 hours of notification of any reactions thought definitely, possibly, or probably related to the VRC07-523LS infusion.

Infusion Site reaction

Infusion Site Erythema or Redness and Infusion Site Induration or Swelling will not be considered interference with usual social and functional activities such that:

- Grade 1 is: 2.5 to < 5 cm in diameter OR 6.25 to < 25 cm² surface area;
- Grade 2 is: ≥ 5 to < 10 cm in diameter OR ≥ 25 to < 100 cm² surface area;
- Grade 3 is: ≥ 10 cm in diameter OR ≥ 100 cm² surface area OR Ulceration OR Secondary infection OR Phlebitis OR Sterile abscess OR Drainage;
- Grade 4 is: Potentially life-threatening consequences (e.g., abscess, exfoliative dermatitis, necrosis involving dermis or deeper tissue)

Allergic or Hypersensitivity Reactions

Record all allergic and hypersensitivity reactions with both grade severity and attribution.

Serious allergic or hypersensitivity reactions (≥ Grade 3) that are deemed possibly related to the study treatment by the study PI (or designee) will be reported to the protocol team and SMC within 24 hours of notification and to the NIH, UNC IRB, FDA, and study product sponsors within 48 hours per their reporting requirements.

Dose Limiting Toxicity (DLT)

- Hematologic dose-limiting toxicity will be defined as any confirmed toxicity ≥ Grade 2, that cannot clearly be attributed to another reversible cause. These participants will not receive further doses of VOR or VRC07-523LS.
- Follow participants per protocol schedule of events until the lab abnormality or toxicity resolves to ≤ Grade 1 or the participant's baseline.
- Non-hematologic dose-limiting toxicity will be defined as any confirmed symptomatic ≥ Grade 3, if related (definitely, probably, or possibly) to VOR or VRC07-523LS

Monitoring HIV RNA levels

In the event of viremia of ≥ 50 copies/mL the following should occur per standard of care:

- Adherence to ART should be carefully assessed and documented.
- A standard HIV RNA assay should be repeated within 1-4 weeks.
- HIV resistance testing will be performed at the time of drawing a confirmatory sample.
- HIV RNA will be repeated every 2 weeks, or sooner as clinically indicated, until <50 copies/mL and the participant can continue on study.
- If persistent viremia is documented, ongoing administration of study treatment will be reviewed on a case-by-case basis with the participant, their HIV provider, and the study team.

In the event of confirmed viremia and documented adherence to ART, ART should be managed by the primary care provider in discussion with the study team. The results of the HIV resistance tests will be shared with the participants and their care providers.

Immediately Reportable Events

Immediately Reportable Events (IREs) are events that must be reported immediately to the sponsor within 24 hours of the study site's awareness of the event:

- All SAEs
- Pregnancy in a study participant or partner of a study participant

- All \geq Grade 2 Cytokine Release Syndrome/Infusion-Related Reactions
- Administration of a dose significantly greater (specifically, + 20 % or higher) than the planned dose, and results in an event of clinical consequence
- AEs leading to permanent discontinuation of study drug in an individual participant
- Withdrawal of the participant from study drug administration during or after receipt of any doses of VRC07-523LS or VRC07-523LS in combination with VOR for any reason
- Product quality issues with an associated clinical consequence.

In those cases, in which the IRE is considered related to study drug, the study drug may be discontinued and the participant will continue participation in the study for observational safety and analysis (except for cases where the participant is withdrawn from the study by the study PI (or designee) or withdrew their consent). At any time after completion of the study, if an Investigator becomes aware of a serious adverse event that s/he suspects is related to study drug, the study PI (or designee) should report the event to NIH, VRC, Merck, FDA, and the UNC IRB, if applicable.

The study PI (or designee) is responsible for appropriate reporting of AEs to the regulatory authorities.

The Protocol Core Team will monitor the conduct and safety of the study via monthly meetings and regular summaries. Accrual, baseline characteristics, conduct of the study (including premature study discontinuations), any interruptions of ART, virologic failures, and all reported toxicities and events will be monitored during the study and discussed with the protocol team on a monthly basis or more frequently, if needed.

The study protocol team will review the individual safety data monthly to assess relation of all reported toxicities and AEs to the study treatment. A study unique independent Safety Monitoring Committee (SMC) will receive monthly study progress and safety monitoring reports. Study feasibility and the achievement of study milestones will be assessed in these reports.

The DAIDS program and medical officers will review and assess the monthly safety reports, as well as EAE reports for potential impact on the study participant safety and protocol conduct as per DAIDS policies, guidance documents, and SOPs, as applicable.

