9.4.4 SAFETY ANALYSES

For the safety endpoint, we will describe all study treatment-related AEs through the end of study approximately 20 weeks after getting their first infusion at Day 0. AEs will be coded to the Medical Dictionary for Regulatory Activities (MedDRA). Events prior to treatment (e.g., due to study-related procedure) will be listed separately in an appendix to the final clinical study report. The following tables of AE data will be created to summarize the number and percent of participants who experience at least one event of each of the following types:

- All AEs
- Drug-related AEs by severity grade
- AEs by severity grade

- All SAEs (this may be a listing if there are few events)
- Drug-related SAEs
- Fatal AEs (this may be a listing if there are few events)
- AEs that result in study discontinuation
- AEs that lead to withdrawal of study drug
- AEs categorized as AESI and/or IREs
- AEs with severity grade 3 or greater
- Drug-related AEs with severity grade 3 or greater

All of these tables will display the number and percent of participants that experience the given event and will display events by System Organ Class (SOC) and Preferred Term (PT). Events will be displayed alphabetically for SOC and in descending order of overall PT incidence within each SOC.

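### The database entry rule leaves out most unrelated Grade 1-2 adverse events, yet two planned safety tables need them

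*Combined protocol and SAP*

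**What the plan says.** **Capture on forms.** Section 8.3.4 sets no filter: "All AEs occurring while on study must be documented appropriately regardless of relationship". Section 8.3.5 also sends all AEs to the study form and counts all adverse experiences among the safety endpoints.

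**Entry in the database.** Section 8.3.5 then adds a condition: "All AEs will be recorded in the database if any of the following criteria have been met". The list is:
- "Study-related grade" 1 or higher, that is, related events of any grade
- any event of Grade 3 or higher
- "Autoimmune-related AEs regardless of grade"
- HIV viral loads of 50 copies/mL or more
- reactions to the infusion, whatever their grade
- "AEs that led to a change in study intervention regardless of grade"
- serious events and those needing expedited reporting

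**Planned tables.** Section 9.4.4 states: "The following tables of AE data will be created to summarize the number and percent of participants who experience at least one event". The event types it lists include all AEs and AEs by severity grade. Drug-related AEs by grade, AEs of Grade 3 or greater, drug-related AEs of Grade 3 or greater, and SAEs are listed separately. Display is by MedDRA system organ class and preferred term.

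**Other recording rules.** Section 8.1 (Signs and Symptoms Assessments) records post-entry signs and symptoms of Grade 2 or higher, plus those of any grade that are related or that lead to a change in study treatment or ART. Section 10.1.9.1 says that clinical data, AEs included, are entered in the database, and states no filter.

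**The concern.** Two of the tables in 9.4.4 are defined without limit on relatedness or grade. Because the drug-related and Grade 3 or greater versions are listed separately, these two must be meant to show the rest, namely unrelated and low-grade events. Those are the events that the entry rule in 8.3.5 lets drop out. Tables produced from a database that follows 8.3.5 would not contain what their titles promise.

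Safety and tolerability are the primary objective, and the study is open-label with a single treatment. For a Grade 1-2 event with no other trigger, the investigator's relatedness judgement alone decides whether it is entered. A reader who takes the all-AE table at face value would see fewer participants with any event than the trial observed. Mild events judged unrelated, which are part of the tolerability picture, would be missing without any note to say so.

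**Working it through.** The plan states no figure on this point, so there is none to reproduce. The check sets the rules side by side.

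**Step 1: entry rule against planned tables.**

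| Event | Entry required by 8.3.5? | Belongs in the all-AE and by-grade tables of 9.4.4? |
|---|---|---|
| Related, any grade | Yes | Yes |
| Unrelated, Grade 3 or higher | Yes | Yes |
| Unrelated, Grade 1-2, with another listed trigger | Yes | Yes |
| Unrelated, Grade 1-2, no other trigger | **No** | **Yes** |

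The mismatch is confined to the last row. One kind of event is outside it: 8.3.4 says that Grade 1-2 laboratory findings generally need not be reported as AEs unless judged clinically significant. Their absence is not an undercount.

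**Step 2: one event under each rule.** Take an unrelated headache outside the solicited-symptom window, with no other trigger.

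| Rule | Grade 1 | Grade 2 |
|---|---|---|
| 8.1, signs and symptoms | Not called for | Recorded |
| 8.3.4 and 8.3.5, study form | Recorded | Recorded |
| 8.3.5, database | Not required | Not required |
| 10.1.9.1, database | Entered | Entered |
| 9.4.4, all-AE table | Expected | Expected |

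The rules give different answers at both grades. No section says that the tables will be drawn from study forms, or that all AEs means only those meeting the entry criteria.

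**Step 3: what the undercount would look like (illustration only).** The documents give no rates for such events, so both probabilities below are assumptions. Let *n* = 12 (section 9.2), *r* = probability that a participant has at least one AE meeting an entry criterion, and *q* = probability of at least one unrelated Grade 1-2 AE meeting none. Taking the two as independent:

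- expected participants missing from the any-AE row = *n* × *q* × (1 − *r*)
- probability that at least one is missing = 1 − [1 − *q*(1 − *r*)]^12

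| *r* | *q* | True any-AE count | Shown from database | Missing | P(at least one missing) |
|---|---|---|---|---|---|
| 0.8 | 0.2 | 10.1 | 9.6 | 12 × 0.2 × 0.2 = 0.5 | 0.39 |
| 0.5 | 0.5 | 9.0 | 6.0 | 12 × 0.5 × 0.5 = 3.0 | 0.97 |
| 0.3 | 0.8 | 10.3 | 3.6 | 12 × 0.8 × 0.7 = 6.7 | >0.99 |

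A participant who also has a qualifying event still counts in the any-AE row. That protection is weaker in the organ-class and preferred-term rows, where the qualifying event may fall under a different term. The range shows how strongly the result depends on unknown rates; it does not estimate the undercount.

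**Step 4: what is untouched.** The primary endpoint (related, Grade 3 or higher), the pause criteria in 10.1.6 (related Grade 3 or higher events in two or more participants, or a related SAE), and the drug-related, Grade 3 or higher and SAE tables all use events that meet an entry criterion.

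**The case against.** The best defence is that the undercount is conditional. Section 10.1.9.1 has AEs entered from source documents with no filter, and 9.4.4 does not name its data source. On that reading everything might be entered. This stands to the extent that an undercount is not certain. It does not remove the problem: 10.1.9.1 is a general sentence on data handling, 8.3.5 is the specific rule, and the two conflict.

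A second defence is that 9.4.4 opens by framing the safety endpoint as treatment-related AEs, which are fully captured. That is true, and it limits the consequence, but the same section goes on to promise two tables with no such restriction.

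Three stronger readings are tempting, and the documents do not support them.
- **A reader might infer that the undercount equals the share of mild and moderate events judged unrelated.** The tables count participants, not events, and the documents give no such share.
- **A reader might infer that the Safety Monitoring Committee could not re-examine attribution.** Section 8.3.4 keeps every AE on record with its severity and relationship. Section 8.3.5 has the protocol team review individual safety data monthly and sends the committee monthly safety reports. Section 10.1.6 has the committee review safety data as they accrue. None of these is limited to database entries. Section 8.3.3.2 also counts a possible link as related, and its only unrelated category requires a documented alternative cause, so a plausible mild drug effect should be entered.
- **A reader might infer that the AE rates could not be compared with those of other studies.** The documents do not describe other studies' entry rules.

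**Conclusion.** The point holds as a mismatch between a stated data-entry rule and two planned tables. Under 8.3.5 an unrelated Grade 1-2 AE with no other trigger need not reach the database. If the all-AE and by-grade tables are built from that database, they will undercount participants with such events and their titles will be wrong. This rests on two assumptions: that the tables come from the database, and that the specific rule in 8.3.5 governs over the general sentence in 10.1.9.1.

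The size cannot be derived from the documents. The illustrative 0.5 to 6.7 of 12 participants reflects assumed rates and independence, nothing more.

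The consequence is limited to descriptive tables. The omitted events are recoverable from study forms, provided that 8.3.4 and 8.3.5 are followed for form capture and not the narrower rule in 8.1. It is still worth correcting before the data are tabulated, because safety is the trial's primary purpose and the remedy is cheap.

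**What to change.** Preferred: amend 8.3.5 so that every AE recorded on the study form is entered in the database and MedDRA-coded. The cost is a little more data entry and coding for about 12 participants, from forms that the protocol already requires.

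Alternative: keep the filter, and retitle or footnote the two tables in 9.4.4 as AEs meeting the entry criteria of section 8.3.5, with those criteria stated. This costs only a change of wording, but the tables will then not describe unrelated mild and moderate events.

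Either way, reconcile the signs-and-symptoms rule in 8.1, the entry criteria in 8.3.5 and the data-entry sentence in 10.1.9.1, so that one rule says what goes on the form and one says what goes in the database. State in 9.4.4 which source the tables use.
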